3.1. Discussion of study design

A cross-sectional study design is the simplest approach to describe the burden of disease, *i.e.* bacterial aetiology of chronic LRTI symptoms. BAL is routinely performed for diagnosis of infection in children with such chronic symptoms, and it is unlikely to be performed repeatedly for otherwise healthy children. Thus, extended follow-up would not be possible.

Considering the invasive nature of the BAL fluid sampling procedure, it has been decided to enrol only those subjects with suspected chronic LRTIs who have BAL procedure indicated by their clinician as part of the local routine diagnostic procedure. This should facilitate subject recruitment and increase participation rates. Nasopharyngeal swabs may not be systematically collected in routine practice. However, since the patient will be under sedation to undergo BAL, he/she will not be subject to additional discomfort or risk due to the swabbing procedure. Thus, it is not expected to affect the willingness of the parent(s)/ LAR(s) to allow their child's participation in this study.

3.2. Case definitions

- **Suspected chronic LRTIs where BAL is indicated:**

Based on clinical and/or radiological symptoms, suspected chronic LRTI will be defined as follows:

- Persistent or recurrent respiratory signs/ symptoms that do not respond to usual treatment:
 - i. *Wet cough* lasting > 4 weeks without additional associated symptoms
 - ii. Recurrent (≥ 3 episodes/ year) or persistent *wheezing* (lasting > 3 months)
 - iii. Persistent *pathologic auscultation* (apart from wheezing) (lasting > 4 weeks).

AND/OR

- Persistent (> 1 month) or recurrent (≥ 3 occurrences/ year) infiltrates/ atelectasis observed on chest radiograph.

Episode of Wheezing: Being previously healthy, and now presenting pathological auscultation with wheezing during long expiration as the main feature.

Evidence of infiltrate/ atelectasis: The presence of new radiological lung condensation, following radiological evidence of normalisation (between two occurrences).

4. STUDY POPULATION

4.1. Number of subjects/ centres

Overview of the recruitment plan:

- This study will be conducted in at least 5 hospitals in Spain.
- The study population will include subjects aged ≥ 6 months to < 6 years visiting the study hospital with suspected chronic LRTIs and for whom BAL sampling will be performed as per the recommendation of the clinician.
- Information on demography and medical history of the subject will be collected. BAL samples and nasopharyngeal swabs will be obtained for this study.
- At least 150 subjects are planned to be enrolled in the study based on the sample size estimation. Refer to section 7.2 for a detailed description of the criteria used in the estimation of sample size.
- The duration of the study will be approximately 2 years from the study initiation. There will be a single visit for each subject.
- A GSK study staff member or delegate will be responsible for monitoring the study.

4.2. Inclusion criteria for enrolment

All subjects must satisfy ALL the following criteria at study entry:

- Subjects who the investigator believes that parent(s)/ LAR(s) can and will comply with the requirements of the protocol.
- A male or female subject aged ≥ 6 months to < 6 years at the time of enrolment.
- Subjects meet the case definition of suspected chronic LRTIs where BAL is indicated (as listed under Section 3.2).
- Subject's parent(s)/ LAR(s) agree to the collection of a nasopharyngeal swab from the subject.
- Written informed consent obtained from the parent(s)/ LAR(s) of the subject.

4.3. Exclusion criteria for enrolment

The following criteria should be checked at the time of study entry. If ANY exclusion criterion applies, the subject must not be included in the study:

- Known cystic fibrosis, immunosuppression, or other severe immunodeficiencies such as agammaglobulinaemia, T cell deficiency or Human Immunodeficiency Virus (HIV)/ Acquired Immune Deficiency Syndrome (AIDS), chemotherapy treatment, etc.

- Exacerbation of persistent respiratory symptoms (cough, wheezing, difficulty in breathing, etc) in the previous 2 weeks. Please refer to Section 3.2 for the definition of exacerbation of persistent respiratory symptoms.
- Antibiotic treatment in the 2 weeks prior to study entry.
- Concurrent participation in another study within 30 days prior to study entry or at any time during the study period, in which the subject has been or will be exposed to an investigational or a non-investigational product (pharmaceutical product or device).
- Subjects having previously participated in this study.
- Child in care. Please refer to the [GLOSSARY OF TERMS](#) for the definition of child in care.

A list of criteria that may eliminate subjects from according to protocol (ATP) analyses can be found in Section 7.3.

5. CONDUCT OF THE STUDY

5.1. Regulatory and ethical considerations, including the informed consent process

The study will be conducted in accordance with all applicable regulatory requirements.

The study will be conducted in accordance with the International Conference on Harmonisation (ICH) Guideline for Good Clinical Practice (GCP) or other applicable guidelines, all applicable subject privacy requirements and the guiding principles of the Declaration of Helsinki.

The study has been designed and will be conducted in accordance with the ICH Harmonised Tripartite Guideline for clinical investigation of medicinal products in the paediatric population (ICH E11) and all other applicable ethical guidelines.

GSK will obtain favourable opinion/approval to conduct the study from the appropriate regulatory agency, in accordance with applicable regulatory requirements, prior to a site initiating the study in that country or will document that neither a favourable opinion nor an approval to conduct the study is needed.

Conduct of the study includes, but is not limited to, the following:

- Institutional Review Board (IRB)/Independent Ethics Committee (IEC) review and favourable opinion/ approval of study protocol and any subsequent amendments.
- Subject's parent(s)/LAR(s) informed consent.
- Investigator reporting requirements as stated in the protocol.

GSK will provide full details of the above procedures to the investigator, either verbally, in writing, or both.

Freely given and written informed consent must be obtained from each subject's parent(s)/LAR(s), as appropriate, prior to participation in the study.

GSK Biologicals will prepare a model Informed Consent Form (ICF) which will embody the applicable ICH GCP and GSK Biologicals required elements. While it is strongly recommended that this model ICF be followed as closely as possible, the informed consent requirements given in this document are not intended to pre-empt any local regulations which require additional information to be disclosed for informed consent to be legally effective. Clinical judgement, local regulations and requirements should guide the final structure and content of the local version of the ICF.

The investigator has the final responsibility for the final presentation of the ICF, respecting the mandatory requirements of local regulations. The ICF generated by the investigator with the assistance of the sponsor's representative must be acceptable to GSK Biologicals and be approved (along with the protocol, and any other necessary documentation) by the IRB/IEC.

Prior to the BAL procedure, the investigator will also ask the subject's parent(s)/LAR(s) to sign a hospital ICF with the details of the BAL sampling procedure. This hospital ICF is independent of GSK and allows a parent to decide on routine clinical care as separate from study participation.

5.2. Subject identification

Subject numbers will be assigned sequentially to subjects who will be included in the study, according to the range of subject numbers allocated to each study centre.

5.3. General study aspects

Supplementary study conduct information not mandated to be present in this protocol is provided in the accompanying Study Procedures Manual (SPM). The SPM provides the investigator and the site personnel with administrative and detailed technical information that does not impact the safety of the subjects.

5.4. Outline of study procedures

Table 3 presents the list of study procedures.

Table 3 List of study procedures

Epoch	Prospective data collection
Visit	VISIT 1
Timing	Day 0
Check inclusion and exclusion criteria	●
Informed consent and subject number attribution	●
Demographic data	●
Collection of data such as clinical characteristics (medical history, chronic LRTI symptoms), vaccination history, feeding and day care practice, environmental exposure and smoking environment	●
Physical examination data	●
Collection of radiological and laboratory results (if available)	●
Collection of BAL fluid samples that were obtained as per routine practice and nasopharyngeal swabs	●
Send BAL fluid and nasopharyngeal swab samples to designated laboratory for microbiological analysis	○
Reporting of SAEs related to the study procedure	●
Laboratory results transcription to database	○
Study conclusion	●
Collection of aggregated data from logbooks	●*

BAL: Bronchoalveolar lavage

● is used to indicate a study procedure that requires documentation in the individual eCRF.

○ is used to indicate a study procedure that does not require documentation in the individual eCRF.

*Aggregated data will be documented in the aggregated logbook module on a monthly basis

5.5. Detailed description of study procedures

5.5.1. Collection of aggregated data from logbooks

A logbook will be maintained at the study hospitals in which aggregated data on the following will be recorded during the entire study period by year of age, on a monthly basis:

- Total number of children presenting to the hospital with an indication for BAL.
- Total number of children presenting to the hospital with an indication for BAL that may be attributable to chronic LRTI.
- Total number of children presenting to the hospital with suspected chronic LRTI who have an indication for BAL and are not enrolled due to applying exclusion criteria.
- Total number of children presenting to the hospital and not being enrolled in the study due to refusal of consent by their parent(s)/ LAR(s).

5.5.2. Procedures prior to study participation**5.5.2.1. Check inclusion and exclusion criteria**

Check all applicable inclusion and exclusion criteria as described in Sections 4.2 and 4.3 before enrolment.

5.5.2.2. Informed consent

Before performing any other study procedure, the signed informed consent of the subject's parent(s)/ LAR(s) needs to be obtained. Refer to Section 5.1 for the requirements on how to obtain informed consent.

5.5.3. Procedures during study participation**5.5.3.1. Subject number attribution**

Once a subject meets the eligibility requirements and has been included into the study, a unique subject number will be assigned. This subject number will be used to uniquely identify all data collected on the subject for the study.

Subject numbers will be assigned sequentially to all subjects, according to the range of subject numbers allocated to each study centre.

5.5.3.2. Collect demographic data

The parent(s)/ LAR(s) of the subject will be interviewed to collect demographic data such as age and gender.

Collected information needs to be recorded in the eCRF.

5.5.3.3. Clinical characteristics and other information

For all subjects aged ≥ 6 months to < 6 years visiting the study hospital with suspected chronic LRTIs, the following information will be recorded, but will not be limited to:

- Clinical characteristics (including medical history, chronic LRTI symptoms),
- Vaccination history,
- Feeding and day care practice,
- Environmental exposure and smoking environment.

5.5.3.4. Collect physical examination data

A physical examination of the subject will be performed as per routine practice, which will include assessment of body temperature, heart rate, respiratory rate after at least 10

minutes of rest, blood pressure and oxygen saturation; the results will be collected as part of this study.

Collected information needs to be recorded in the eCRF.

5.5.3.5. Radiological and laboratory results

For all subjects aged ≥ 6 months to < 6 years visiting the study hospital with suspected chronic LRTIs, radiological and laboratory results will be collected, if available. Findings from the chest X-ray, (if present) will also be recorded.

If results of blood testing are available from routine practice, then data on white blood cell counts, CRP level and erythrocyte sedimentation rate, etc will be recorded in the eCRF.

5.5.3.6. Collection of BAL fluid samples and nasopharyngeal swabs

Following routine BAL procedures at the hospital, the second aliquot of BAL fluid that is obtained will be sent to the GSK designated laboratory for microbiological analysis.

Nasopharyngeal swabs will be collected as part of this study. Collected samples will also be sent to the GSK designated laboratory for microbiological analysis.

5.5.3.7. Recording of Serious Adverse Events

- The subjects' parent(s)/LAR(s) will be instructed to contact the investigator immediately should the subjects manifest any signs or symptoms they perceive as serious.

Refer to Section 6.2 for procedures for the Investigator to record serious adverse events (SAEs) that are related to study participation and to Section 6.3 for guidelines on how to report these SAEs to GSK Biologicals.

5.5.3.8. Study conclusion

The investigator will review the data collected to ensure accuracy and completeness and will complete the Study Conclusion screen in the eCRF.

5.6. Biological Sample handling and analysis

Please refer to the SPM for details of biospecimen management (handling, storage and shipment).

Samples will not be labelled with information that directly identifies the subjects but will be coded with the identification number for the subject (subject number).

Collected samples may be used in other assays, for test improvement or test development of analytical methods related to the disease under study to allow to achieve a more

reliable measurement. Under these circumstances, additional testing on the samples may be performed by GSK Biologicals outside the scope of this protocol.

Information on further investigations and their rationale can be obtained from GSK Biologicals.

Any sample testing will be done in line with the consent of the individual subject's parent(s)/ LAR(s).

Any human pharmacogenetic testing will require specific consent from the individual subject's parent(s)/ LAR(s) and the ethics committee approval. Any human immunodeficiency virus (HIV) testing will also require specific consent and ethics committee approval.

Refer also to the [Investigator Agreement](#), where it is noted that the Investigator cannot perform any other biological assays except those described in the protocol or its amendment(s).

Collected samples will be stored for up to 15 years (counting from when the last subject performed the last study visit), unless local rules, regulations or guidelines require different timeframes or different procedures, which will then be in line with the subject consent. These extra requirements need to be communicated formally to and discussed and agreed with GSK Biologicals.

For routine sample collection when coded sample is shipped to GSK and needs to be linked to coded subject data, (re-) consent from the subjects and/or IEC/IRB approval will be sought.

5.6.1. Use of specified study materials

When materials are provided by GSK Biologicals, it is MANDATORY that all samples be collected and stored exclusively using those materials in the appropriate manner. The use of other materials could result in the exclusion of the subject from the ATP analysis (See Section 7.3 for the definition of study cohorts to be evaluated). The investigator must ensure that his/her personnel and the laboratory(ies) under his/her supervision comply with this requirement. However, when GSK Biologicals does not provide material for collecting and storing samples, appropriate materials from the investigator's site must be used. Refer to the Module on Clinical Trial Supplies in the SPM.

5.6.2. Biological samples

[Table 4](#) presents the biological samples that will be collected for this study.

Table 4 Biological samples

Sample type	Quantity	Time point
BAL	At least 2 mL	Visit 1
Nasopharyngeal swab	1 swab	Day 0

5.6.3. Laboratory assays

Laboratory assays to characterise BAL fluid and nasopharyngeal swab samples including the detection of *S. pneumoniae*, *H. influenzae* and *M. catarrhalis* will be performed by standard techniques at GSK Biologicals' laboratory or in a validated laboratory designated by GSK Biologicals using standardised and validated procedures (refer to Table 5).

Table 5 Laboratory assays (Amended 05 October 2015)

Pathogen/ Marker	Method	Scale		Sample type	
		Qualitative	Quantitative	BAL	NP
Identification and/ or quantification of bacteria					
S. pneumoniae	Culture		X	X	X
	Molecular techniques (PCR)		X		
H. influenzae	Culture		X	X	X
	Molecular techniques (PCR) (differentiation between Hi and Haemophilus haemolyticus)†		X		
M. catarrhalis	Culture		X	X	X
	Molecular techniques (PCR)		X		
Other pathogens (if detected)	Culture	X		X	X
Serotyping of bacterial pathogens					
S. pneumoniae	Agglutination assay or molecular techniques	X		X	X
H. influenzae	Monovalent antisera	X		X	X
Antibiotic sensitivity : Including penicillin, erythromycin, azithromycin, tetracycline, levofloxacin, trimethoprim/ sulfamethoxazole, amoxicillin/ clavulanate susceptibility testing for H. influenzae, S. pneumoniae and M. catarrhalis isolated from BAL and NP swab samples; and additionally a beta-lactamase test for H. influenzae and M. catarrhalis isolated from BAL and NP swab samples; and ampicillin resistance testing by broth microdilution for beta-lactamase negative H. influenzae isolated from BAL and NP swab samples.					

†: PCR differentiation between Hi and *H. haemolyticus* will be performed on isolates from BAL/ NP swab samples that are *H. influenzae* positive

Collected samples will be used for purposes related to the quality assurance of data generated within the scope of this protocol, such as for maintenance of assays described in this protocol and comparison between analytical methods and/or laboratories.

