2.2. Secondary objectives

In a hospital setting and among subjects with suspected chronic LRTIs:

- To describe the bacterial load of *H. influenzae*, *S. pneumoniae* and *M. catarrhalis* detected by quantitative culture and by molecular techniques (PCR) in the BAL fluid.
- To describe the presence of other bacterial pathogens detected by qualitative culture in the BAL fluid.
- To describe the bacterial load of *H. influenzae*, *S. pneumoniae* and *M. catarrhalis* detected by quantitative culture and by molecular techniques (PCR) in the nasopharyngeal swab samples.
- To describe the presence of other bacterial pathogens detected by qualitative culture in the nasopharyngeal swab samples.
- To describe colonisation of the upper airways by characterising *H. influenzae*, *S. pneumoniae*, *M. catarrhalis* and other pathogens in nasopharyngeal swab samples.
- To determine the serotypes of *H. influenzae* and *S. pneumoniae* identified from BAL fluid samples.
- To determine the serotypes of *H. influenzae* and *S. pneumoniae* identified from nasopharyngeal swab samples.
- To determine the antibiotic susceptibility profile for *H. influenzae*, *S. pneumoniae* and *M. catarrhalis* identified from BAL fluid **and nasopharyngeal swab** samples. (Amended 05 October 2015)
- To describe, according to microbiological results observed:
 - Age and gender
 - Clinical symptoms and radiological evidence
 - Pneumococcal conjugate vaccine, *H. influenzae* type b vaccine and influenza vaccine status

- Medical history and co-morbidities
- Information on feeding and day care practice, environmental exposure and smoking environment
- History of antibiotic use in the past six months as well as other treatments for chronic lower respiratory disease
- Laboratory results [including white blood cell counts, C-Reactive Protein (CRP) level and erythrocyte sedimentation rate, if available].

Refer to Section 7.1.2 for the definition of the secondary endpoints.

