7.1.2. Secondary endpoints

In a hospital setting and among subjects aged ≥ 6 months to < 6 years with suspected chronic LRTIs and an indication for BAL:

- Bacterial load of *H. influenzae*, *S. pneumoniae* and *M. catarrhalis* in the BAL fluid as determined by quantitative culture and PCR.
- Description of other bacterial pathogens in the BAL fluid as determined by qualitative culture.
- Bacterial load of *H. influenzae*, *S. pneumoniae* and *M. catarrhalis* in nasopharyngeal swab samples as determined by quantitative culture and PCR.
- Description of other bacterial pathogens in nasopharyngeal swab samples as determined by qualitative culture.
- Occurrence of *H. influenzae*, *S. pneumoniae*, *M. catarrhalis* and other pathogens detected by culture in the nasopharyngeal swab samples.
- Occurrence of *H. influenzae* and *S. pneumoniae* serotypes identified from BAL fluid samples and nasopharyngeal swab samples.
- Occurrence of *H. influenzae*, *S. pneumoniae* and *M. catarrhalis* minimum inhibitory concentration (MIC) values identified from BAL fluid **and nasopharyngeal swab** samples. (Amended 05 October 2015)
- Demographic characteristics (age, gender, etc), clinical characteristics (including medical history, LRTI symptoms, treatment history, vaccination status, etc),

[figure not shown]
radiological evidence and laboratory results (including white blood cell counts, CRP level and erythrocyte sedimentation rate, if available).

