7.6.3. Analysis of secondary objectives

The distribution (with number of non-missing observations, geometric mean, standard deviation, median, minimum and maximum and number of missing observations) of the bacterial load of *H. influenzae*, *S. pneumoniae*, *M. catarrhalis* and other pathogens will be described according to the testing method (culture or PCR) and to the samples (BAL fluid sample or nasopharyngeal swab sample).

The serotype distribution (number and percentage) of *H. influenzae* **and** *S. pneumoniae* detected in BAL fluid will be presented in frequency tables.

The bacterial aetiology and serotype distribution of nasopharyngeal samples will be described along with that of BAL fluid samples.

The proportions and associated exact 2-sided 95% CI of *H. influenzae*, *S. pneumoniae*, *M. catarrhalis* and other bacterial pathogens confirmed by culture in nasopharyngeal swab will be computed for all study subjects.

For the antibiotic susceptibility, *H. influenzae*, *S. pneumoniae* **and** *M. catarrhalis* isolates (detected by culture of BAL fluid **and nasopharyngeal swab**), classified as susceptible, intermediate or resistant (following ***Clinical and Laboratory Standards Institute*** guidelines [***CLSI, 2015***]) will be tabulated by bacterial pathogen and antimicrobial agent.

(Amended 05 October 2015)

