6.3. Analysis of secondary objectives

All tables related to secondary objectives 1 to 8 will be presented overall as well as by age class, gender, pneumococcal vaccination status. The age will be grouped into the following classes 6-11, 12-23, 24-35, 36-47, 48-59 and 60-71 months; however, if there are too few subjects in any of the categories, the following classification will be used of 6-23, 24-47, 48-71 months instead.

In a hospital setting and among subjects with suspected chronic LRTIs:

- 1) To describe the bacterial load of *H. influenzae*, *S. pneumoniae* and *M. catarrhalis* detected by quantitative culture and by molecular techniques (PCR) in the BAL fluid.

The distribution (with number of non-missing observations, geometric mean, standard deviation, median, minimum and maximum and number of missing observations) of the bacterial load of *H. influenzae*, *S. pneumoniae*, *M. catarrhalis* in the BAL fluid will be described according to the testing method (culture and PCR).

- 2) To describe the presence of other bacterial pathogens detected by qualitative culture in the BAL fluid.

The presence (number and percentage) of other bacterial isolates detected in BAL fluid will be presented in frequency tables.

- 3) To describe the bacterial load of *H. influenzae*, *S. pneumoniae* and *M. catarrhalis* detected by quantitative culture and by molecular techniques (PCR) in the nasopharyngeal swab samples.

The distribution (with number of non-missing observations, geometric mean, standard deviation, median, minimum and maximum and number of missing observations) of the bacterial load of *H. influenzae*, *S. pneumoniae*, *M. catarrhalis* in the nasopharyngeal swab samples will be described according to the testing method (culture and PCR).

- 4) To describe the presence of other bacterial pathogens detected by qualitative culture in the nasopharyngeal swab samples.

The presence (number and percentage) of other bacterial isolates detected in the nasopharyngeal swab samples will be presented in frequency tables.

- 5) To describe colonisation of the upper airways by characterising *H. influenzae*, *S. pneumoniae*, *M. catarrhalis* and other pathogens in nasopharyngeal swab samples.

Statistical Analysis Plan

Study alias & e-track number(s): EPI-STREP-064 BOD ES (115813)

The occurrence of *H. influenzae*, *S. pneumoniae*, *M. catarrhalis* and other pathogens detected by culture in the nasopharyngeal swab samples will be presented:

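### Does the isolate footnote in protocol Table 5 leave the study without an H. influenzae PCR load in BAL fluid and swabs?

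*Protocol*

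**What the plan says.** Protocol section 2.2 sets out to describe the load of H. influenzae, S. pneumoniae and M. catarrhalis "detected by quantitative culture and by molecular techniques (PCR) in the BAL fluid", with a matching objective for swabs. Section 7.1.2 turns these into endpoints: load "in the BAL fluid as determined by quantitative culture and PCR" and load "in nasopharyngeal swab samples as determined by quantitative culture and PCR". SAP section 4.2 repeats both.

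The analysis sections follow suit. Protocol section 7.6.3 says the distribution of load "will be described according to the testing method (culture or PCR) and to the samples". SAP section 6.3, items 1 and 3, says the load "in the BAL fluid will be described according to the testing method (culture and PCR") and "in the nasopharyngeal swab samples will be described according to the testing method (culture and PCR"). Each calls for counts of non-missing and missing observations.

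Protocol Table 5 lists the assays. S. pneumoniae and M. catarrhalis each have a culture line and a plain PCR line, all marked quantitative. H. influenzae has the same two lines, also marked quantitative, but its PCR line is labelled "Molecular techniques (PCR) (differentiation between Hi and Haemophilus haemolyticus") and carries a dagger. The dagger note is "PCR differentiation between Hi and *H. haemolyticus* will be performed on isolates from BAL/ NP swab samples that are *H. influenzae* positive". The H. influenzae serotyping row lists antisera only, so no second H. influenzae PCR appears in the table.

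**The concern.** Taken literally, the only H. influenzae PCR in the study would be run on colonies grown from samples that had already tested positive. That cannot serve endpoints 1 and 3. A PCR on a colony says which species it is, not how much was in the sample, and a culture-negative sample has no colony to test.

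Three consequences would follow:

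- PCR could never find H. influenzae where culture had missed it.
- The PCR summaries for the three organisms would stand side by side although they covered different sets of children.
- The SAP's missing count would mix samples never tested with tests that failed.

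The choice of which samples go to PCR is made in the laboratory, so it is fair to ask about it before the analysis. Two smaller questions come with it: how to label a sample that is PCR positive but culture negative, and how to count an isolate that the species test calls H. haemolyticus. The SAP does not mention that organism.

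**Working it through.** **The plan's own figures.** Protocol section 7.2 gives exact 95% intervals for 150 subjects. The Clopper-Pearson lower limit is the 0.025 quantile of Beta(x, n − x + 1). The upper limit is the 0.975 quantile of Beta(x + 1, n − x).

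- x = 17, n = 150: 11.33%, interval 6.74% to 17.52% (plan: 11.3%, 6.7 to 17.5).
- x = 50, n = 150: 33.33%, interval 25.86% to 41.48% (plan: 33.3%, 25.9 to 41.5).

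Both reproduce. Neither depends on PCR.

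**Size under the literal reading.** Take 150 subjects and the 7% to 51% expected for H. influenzae in section 7.2, and assume that this is the share of BAL samples yielding an isolate.

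- With an isolate: 150 × 0.07 = 10.5; 150 × 0.51 = 76.5.
- Without: 150 − 10.5 = 139.5 (93%); 150 − 76.5 = 73.5 (49%).

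These figures look large but do not measure the problem, for two reasons. First, if colony PCR gives no sample load, the literal reading leaves 0 of 150 subjects with a PCR load, not 10.5 to 76.5. A column filled for culture-positive children and empty for the rest cannot arise on that premise. Second, the 51% matches a Table 1 row (51.2%, recurrent pneumonia) that applied a cut-off of at least 10^4 CFU/mL. Growth below a cut-off still gives an isolate, so the count without one could be smaller. For swabs the documents give no expected proportion.

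**Size under the two-assay reading** (quantitative PCR on every sample, species test on isolates): untested by design = 150 − 150 = 0, as for the other two organisms.

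**Which reading fits the text.**

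| Text | One assay, isolates only | Two assays |
|---|---|---|
| Grammatical subject of the dagger note: differentiation | Must be stretched to cover quantification | Fits |
| PCR line marked quantitative | Conflicts: telling two species apart is qualitative | Fits |
| Line sits in the identification and quantification block | Awkward | Fits |
| Objectives, endpoints and analyses in both documents | Conflicts | Fits |
| One line and one label in Table 5 | Fits | Untidy |

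**History, as evidence of intent only.** In Appendix A, the Table 5 shown under Amendment 1 has a plain quantitative PCR line for H. influenzae. The differentiation step stands apart in the serotyping row with the same dagger note. Amendment 2 places that label on the PCR line. Its stated reasons concern susceptibility, beta-lactamase and ampicillin testing, alignment of the secondary endpoints, and general tidying. Nothing there withdraws PCR quantification of H. influenzae. The same amendment rewrote the synopsis endpoints to include PCR load for all three organisms.

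**The case for a change.** The best argument for acting is that the documents do not exclude the literal reading. Table 5 is the only list of assays, it shows one H. influenzae PCR, and the restriction hangs on that line alone. Section 5.6.2 requires only at least 2 mL of BAL fluid and one swab, so later testing could be short of material. One question to the laboratory and a split table line would cost almost nothing.

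The two-assay reading also leaves a loose end. The sponsor evidently thinks that separation from H. haemolyticus matters, yet a PCR-positive, culture-negative sample has no isolate on which to do it.

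Part of this stands. The line is badly labelled, and two rows would read better. Neither document spells out the PCR denominator or what happens to an isolate renamed as H. haemolyticus. But these are details that laboratory and analyst settle in the ordinary course:

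- Whether a PCR-positive, culture-negative sample is H. influenzae depends on the assay target. That belongs to the laboratory procedures, which are not among these documents.
- A species test on isolates exists to fix the species name, so the natural course is to count an isolate under the name the test gives. If the laboratory reports species after the test, the effect on the culture proportions is zero. Otherwise the documents give no rate from which to size it.
- If only isolates had been tested, there would be no H. influenzae PCR load for any child, which would be plain when the data arrived. Section 5.6 allows samples to be stored for up to 15 years.

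The wish to predict BAL culture from swabs does not add weight. It appears in the rationale, but no objective, endpoint or analysis carries it.

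**Conclusion.** No change follows. Table 5 runs two H. influenzae assays together under one label. That is a clerical fault, and the rest of the protocol and the SAP resolve it: both require a PCR load measured in the sample, and the footnote limits only the species test. On that reading, 0 of 150 subjects lack an H. influenzae PCR result by design, and the planned tables can be produced as described.

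The conclusion assumes that the laboratory works to the endpoints and the quantitative mark, not to the widest reading of the footnote; the documents cannot prove this. If the assumption failed, the loss would be the H. influenzae PCR summaries under secondary endpoints 1 and 3, which are descriptive. The primary proportions rest on culture (protocol sections 7.1.1 and 7.6.2, SAP section 6.2) and do not use the PCR load.
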